## 4. ANALYSIS SETS

Population	Definition / Criteria	Analyses Evaluated
Safety analysis set	

• All randomised subjects who received at least one dose of HB-adMSCs infusion or placebo.

• If participants receive a treatment different to their randomized treatment, they will be analysed according to the treatment actually received.

	

• Safety

• Study Population

Efficacy analysis set	

• All randomized participants who received all 6 infusions of HB-adMSCs or placebo.

• Participants will be analysed according to their randomized treatment.

	

• Efficacy

Screened Population	

• This population consists of all subjects who signed an ICF to participate in the clinical trial.

• This population will be used for summarizing screening failures and reasons for screening failures.

	

• Study Population

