Other aspects to consider, such as voluntary participation in the clinical study will be followed according to FDA guidance, IRB Guide for Researchers and Sponsor standard operating procedure.

Figure 1 Informed consent timelines.

After Informed consent has been obtained, each participant should complete the following visits.

- Visit 1 – Screening, during this period, the principal investigator will make the decision to determine whether the screened participant is eligible and whether the next visit can be scheduled. Once the principal investigator has evaluated the eligibility of the subject screened (up to 28 days), a randomization process will be conducted to assign the eligible subject either HB-adMSCs or Placebo. Randomization will only apply to eligible subjects. If a study participant does not meet the inclusion criteria during the screening process, he/she will be considered Screen Failure (SF) and does not need to be randomized to any group.
- Visit 2 – Infusion 1, **(Baseline)**: this visit will be used as a starting point for comparison of participant's data. During this visit, eligible study participants will receive his/her first investigational product administration or placebo with a rigorous monitoring of vital signs for a total of 2 hours after drug exposure. Other study evaluations will be completed as part of this visit.
- Visit 3 – Infusion 2: approximately 4 weeks after the initial investigational product administration this visit should be completed. Other study evaluations will be completed as part of this visit.
- Visit 4 – Infusion 3: approximately 8 weeks after the initial investigational product administration this visit should be completed. Other study evaluations will be completed as part of this visit.
- Visit 5 – Infusion 4: approximately 16 weeks after the initial investigational product administration this visit should be completed. Other study evaluations will be completed as part of this visit.

- Visit 6 – Infusion 5: approximately 24 weeks after the initial investigational product administration this visit should be completed. Other study evaluations will be completed as part of this visit.
- Visit 7 – Infusion 6: approximately 32 weeks after the initial investigational product administration this visit should be completed. Other study evaluations will be completed as part of this visit.

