- Visit 8 – Safety Follow Up: approximately 42 weeks after the initial investigational product administration, active study participants will complete a follow up visit at the clinic site.
- Visit 9 – End of Study, during this final visit (approximately 52 weeks after Week 0) a complete group of study assessments will be performed to evaluate the safety and efficacy of HB-adMSCs or Placebo administrations.

Clinical assessments of disease activity will take place during the following visits:

- Visit 1 – Screening
- Visit 2 – Infusion 1 (**Baseline**)
- Visit 4 – Infusion 3
- Visit 6 – Infusion 5
- Visit 8 – Follow Up
- Visit 9 – End of Study

Blood samples for safety assessments will be collected in as follows:

- Visit 1 – Screening: after informed consent has been obtained, blood samples should be collected from a vein of the study's participant arm, these lab results will help assess the subject's eligibility.
- Visit 2 – Infusion 1, (**Baseline**): safety laboratory samples will be collected from the study participant's vein to establish a baseline for comparison with the laboratory results obtained in subsequent visits.
- Visit 6 – Infusion 5: safety laboratory samples should be collected from a vein of the study's participant arm during this visit.

Visit 9 – End of Study: safety laboratory samples should be collected from a vein of the study's participant arm during this visit.

For study participants who do not complete the study trial, a safety follow-up visit will be scheduled as follows:

- For subjects who did not receive any of the investigational products and were eligible to participate in the trial, they will be invited to a safety follow-up visit, or Early termination visit (ETV) within 30 days after the last visit.
- For subjects who received at least one dose of the investigational product, they will be invited to a safety follow-up visit, approximately 30 days following that single treatment.
- For subjects who received more than one dose of the investigational product, they will be invited to a safety follow-up visit, approximately 30 days following the last treatment.

Withdrawal Criteria

In different situations, a study subject may withdraw from the study before the planned completion of the visits. One of these situations is mentioned below,

1. Voluntary withdrawal: subject doesn't want to continue receiving the investigational product.

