9-Hole Peg Test		X		X		X		X	X
Multiple Sclerosis Quality of Life Inventory 54		X		X		X		X	X
Patient Health Questionnaire 9 (PHQ-9)		X							X
Study Treatments Administration		X	X	X	X	X	X		
24 hours Telephone Encounter		X	X	X	X	X	X		
Video Documentation		X				X			X
AE and SAE assessments		X	X	X	X	X	X	X	X

¹ Collection of laboratory samples (CBC, CMP & Coagulation Panel)

Study Visits 1 to 9.

Visit 1 – Screening.

At the Screening Visit (Visit 1), study participants' information will be collected by study's delegated personnel for evaluation of trial eligibility. The following information is required to determine eligibility:

1. Signing Informed Consent Form (prior to any trial-related activities).
2. Collection of demographic information, such as age, race, ethnicity, date of birth, gender, and relevant medical and surgical history.
3. Collection of Medical History and concomitant medications, including relevant information about the past and present health of study participants.
4. Inclusion and Exclusion criteria evaluation.
5. Measurement of vital signs including respiratory rate, body temperature, blood pressure, pulse rate, oxygen saturation, and measurement of weight and height.
6. Collection of laboratory samples, including Comprehensive Metabolic Panel (CMP), Complete Blood Count (CBC), Coagulation Panel, and Urine pregnancy test if female of childbearing potential.
7. Physical examination by Principal Investigator, including clinical assessments such as Expanded Disability Status Scale (EDSS).

Within 28 days of the Visit 1 - Screening, the principal investigator must decide participant's eligibility. Once, the eligibility of the subject has been confirmed by the principal investigator, the randomization process will be conducted.

Visit 2 and 6 – Infusion 1 (Baseline) and Infusion 5

The following procedures are required during this visit:

1. Update medical history and concomitant medications if any change occurred since last visit.
2. Measure vital signs including respiratory rate, body temperature, blood pressure, pulse rate, oxygen saturation and measurement of weight.
3. Collect laboratory samples, including Comprehensive Metabolic Panel (CMP), Complete Blood Count (CBC), Coagulation Panel and Urine pregnancy test if female of childbearing potential.

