If an infusion is stopped for a subject due to an adverse event or serious adverse event, including but not limited to hypersensitivity reaction/anaphylaxis, no additional study treatment will be given to the study participant who develops the event. Although, the study participant will not receive the investigational product, he or she must be followed for safety purposes according to the protocol.

Study Stopping Rules

This Clinical Trial will stop if any of the following events are present:

1. Subject's Death.
2. Occurrence of any thromboembolic event during or after HB-adMSCs administrations (up to 72 hours).
3. Any cerebrovascular ischemia or seizure event occurring within 72 hours after any of the investigational product administrations.
4. Any Serious Adverse Events determined to be related to the following:

- When there is one CTCAE.v5 grade 4 or 5 AE, irrespective of attribution.
- Either any CTCAE Grade 2 adverse event that persists for more than two weeks, or any Grade 3 adverse event, that occurs within 72 hours after product administration.

Should the study participant discontinue study treatment he/she will be followed for safety according to the protocol safety monitoring plan. The study participant will receive follow up communication via phone calls and/or electronically to ascertain the outcome until resolved fully. All will be documented as per protocol.

All changes to the study stopping rules shall be reviewed by FDA. If the study is suspended for any reason, it will not be re-opened until FDA agrees. Regardless of whether the study is stopped or suspended all subjects will be followed to the EOS as per protocol.

Statistical Methods

Sample size consists of up to 24 subjects who have been diagnosed with Relapsing Remitting Multiple Sclerosis. All data collected from subjects who are enrolled and received the investigational product will be analyzed. The incidence of Adverse Events and Serious Adverse Events will be recorded and reported. Efficacy will be measured by improvement of subject's signs and symptoms associated with Multiple Sclerosis. Interim analysis of all safety and efficacy data may be performed at any time deemed appropriate by the Sponsor. Although, the subject's data may be analyzed at any time, a data analysis of all available data will be conducted when a least 10 subjects in each group have completed Week 24. Data may be analyzed for internal informational purposes, reports, presentations, and manuscripts.

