## 5.2. Primary Endpoint(s) Analyses

The primary objective of this study is to compare HB- adMSCs to Placebo on Multiple Sclerosis Quality of Life (MSQOL)-54 Instrument scores. Efficacy analysis set will be used for this analysis. The details of the planned displays are in programming specification document.

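### The only efficacy set keeps participants who received all 6 infusions, so events after randomisation decide who enters the primary comparison, and SAP 5.4 does not declare this narrowing

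*SAP*

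**What the plan says.** SAP Section 4 (Analysis Sets) lists three populations. Only one is assigned to efficacy: "All randomized participants who received all 6 infusions of HB-adMSCs or placebo". Its members are analysed in the arm to which they were randomised. The safety set requires one dose and serves safety and study-population summaries only. SAP Section 7.1.2 refers to a randomised set, but Section 4 does not define it and it is used only for demographics.

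For the primary endpoint, SAP Section 5.2 states: "Efficacy analysis set will be used for this analysis". No sensitivity analysis on a wider set follows.

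The protocol's Statistical Methods section is broader: "All data collected from subjects who are enrolled and received the investigational product will be analyzed". It sets no minimum number of infusions and names no separate efficacy population. SAP Section 5.4 reports that nothing departs from the protocol's analysis.

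On timing, the protocol's Investigational Plan says that after eligibility is assessed at screening, "a randomization process will be conducted to assign the eligible subject either HB-adMSCs or Placebo". Infusion 6 falls at about Week 32 after the first infusion.

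Two protocol rules end dosing early. When an infusion is stopped for an adverse event, "no additional study treatment will be given to the study participant who develops the event" (Infusion Stopping Rules), although that person stays in follow-up. The Withdrawal Criteria give the other: "Voluntary withdrawal: subject doesn't want to continue receiving the investigational product".

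**The concern.** Randomisation makes the arms comparable at the start. A set that can be fixed only some 32 weeks later compares those who got through treatment in one arm with those who got through it in the other. Tolerability and perceived benefit can differ by arm and can relate to later quality of life, so the two groups of completers need not be comparable. Analysing them as randomised within the set does not undo this selection.

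The rule also discards collected data. The Schedule of Assessments row "Multiple Sclerosis Quality of Life Inventory 54" marks Weeks 8, 24, 42 and 52 after baseline. Someone who misses only infusion 6 and stays in follow-up can have all four post-baseline values and still be removed. The repeated-measures model, which could use partial data, is confined to the same set.

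With about 12 per arm, each exclusion is 1/12, about 8% of an arm. The planned disposition tables (SAP 5.1.1 and 7.1.1) would show how many left and why, but nothing planned would show what their removal did to the estimate.

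**Working it through.** **No plan figure to reproduce.** The SAP gives up to 24 participants and 1:1 allocation (about 12 per arm), tested at two-sided 0.05. It gives no SD, effect size, power or dropout rate. The protocol anticipates drop-out when describing the allocation table but gives no rate. What follows is therefore a range under stated assumptions.

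**Step 1: analytic bound.** Assume no true effect and SD of change 15. The test below is unadjusted, so read 15 as the residual SD after the planned adjustment for baseline and strata. Suppose a fraction p of one arm leaves and stopping is perfectly correlated with a poor Week 52 outcome. The mean of those remaining rises by φ(z)/(1−p) SD, with z the p-quantile of the standard normal.

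- p = 2/12: 0.30 SD × 15 = 4.5 points.
- p = 3/12: 0.42 SD × 15 = 6.4 points (unrounded 0.4237 × 15).

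For a lower correlation ρ, multiply by ρ. At ρ = 0.5 this gives about 2.2 and 3.2 points.

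**Step 2: simulation.** 100,000 trials per cell, 12 per arm, no true effect. Each participant stops according to a latent variable with correlation ρ to outcome. Completers are compared by a two-sided t-test at 0.05.

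| Average losses | ρ = 0 | 0.25 | 0.5 | 0.75 | 1 |
|---|---|---|---|---|---|
| Active 2, placebo 0: shift (points) | 0 | 1.1 | 2.2 | 3.4 | 4.5 |
| Type I error (%) | 5.1 | 5.4 | 6.2 | 7.8 | 10.1 |
| Active 3, placebo 0: shift (points) | 0 | 1.6 | 3.2 | 4.7 | 6.3 |
| Type I error (%) | 5.1 | 5.5 | 7.2 | 10.4 | 15.5 |

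Other patterns:

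- Placebo losses only: mirror image, to about −4.5 and −6.4 points.
- Active 2, placebo 1: 0 to 2.0 points, 5.0% to 6.3%.
- Equal losses (2 and 2, or 3 and 3): shift about 0, type I error 4.9% to 5.1%.

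Repeat runs agree within simulation error.

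**Step 3: fixed number removed.** Removing exactly 2 (or 3) active participants at ρ = 1 gives 4.1 (5.9) points and 11.2% (16.3%). Removing exactly 2 from each arm leaves the shift at 0, but type I error is 5.0%, 5.7% and 8.9% at ρ = 0, 0.5 and 1, because cutting off the lowest values makes the observed spread too small.

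**Step 4: effect of using all available data.** 20,000 trials per cell, changes at Weeks 8, 24, 42 and 52 with common correlation 0.5 or 0.7. Two or three active participants stop after Week 24 and have no later values. The completer-only difference is compared with a likelihood-type estimate that regresses Week 52 on Weeks 8 and 24 and so uses everyone.

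- Stopping depends on the observed Week 24 score: a shift of 2.1 to 4.1 points falls to 0.1 or less (0.2 or less in a repeat run).
- Stopping depends on the unseen Week 52 value, ρ = 0.5: 2.1 to 3.0 points falls only to 0.9 to 2.0.

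**The case against.** The strongest objection is about attribution. The planned primary analysis is a Week 52 ANCOVA. For those who leave after more than one dose the protocol says only that "they will be invited to a safety follow-up visit, approximately 30 days following the last treatment". Without a Week 52 score they drop out of the ANCOVA under any set, so widening the set alone would not change its estimate. This stands, and it is why the fix must change the estimator as well as the set. It does not remove the defect. Participants whose infusion was stopped for an adverse event remain in follow-up, so the set can exclude people who do have Week 52 values.

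Second, the large figures are corner cases: one-sided losses and correlation 1. At correlations of 0.25 to 0.5 with 2 active losses, type I error is 5.4% to 6.2%. Blinding makes arm-related voluntary withdrawal less likely, and the study stopping rules could halt the trial in some one-sided adverse-event scenarios. That limits the likely size but does not protect the comparison.

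Third, the protocol sentence on analysing all data is generic. That is fair: the SAP narrows it without saying so, rather than contradicting it outright.

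Fourth, a gain in type I error from the fix has not been demonstrated. A small check of the mixed model (12 per arm, visit correlation 0.6, 2 or 3 active leavers, 410 to 641 runs per cell, margin about 2 to 2.5 percentage points) gave 5% to 8% using t with 18 degrees of freedom and 7% to 10% using z, against 6% to 9% for completer ANCOVA. The shift fell, but the error rates could not be told apart. The choice of degrees of freedom therefore matters at this sample size.

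**Conclusion.** The concern holds and should be fixed before unblinding. On the text there is no doubt: one efficacy set, fixed at infusion 6, used for the primary analysis, with no wider analysis and no declaration in SAP 5.4. The size and direction of any bias cannot be determined from the documents.

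Under the assumptions above, one-sided losses averaging 2 or 3 of 12 move the difference by anything from nothing to roughly 4.5 or 6.4 points, towards or away from HB-adMSCs depending on which arm loses participants. Type I error rises from about 5% to about 10% or 15.5% at the extreme. At a correlation of 0.5 the figures are 2.2 or 3.2 points and 6.2% or 7.2%. If losses are unrelated to outcome, or balanced and alike in the two arms, the difference is not shifted and the main cost is lost data.

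**What to change.** - **SAP Section 4.** Define the primary efficacy set as all randomised participants (at minimum all treated, in line with the protocol), analysed as randomised. Use every available post-baseline MSQOL-54 value, including those after infusions stop. Count and list by arm anyone without a post-baseline value, and state how a missing baseline is handled: MSQOL-54 is first scheduled at Visit 2, and SAP 5.1.2 leaves an absent baseline missing.
- **SAP Sections 5.2 and 5.2.2.** Take the Week 52 treatment contrast from the repeated-measures model already planned, a model type the protocol's Statistical Methods section itself names, fitted at Weeks 8, 24, 42 and 52, where the score is collected. State the degrees-of-freedom method. The lesser option is to keep the ANCOVA primary and name this contrast as its pre-specified check, but the ANCOVA would then still omit leavers without a Week 52 score.
- **Sensitivity analysis.** Keep the 6-infusion set as a labelled per-protocol analysis.
- **SAP Section 5.4.** Declare any efficacy set narrower than the protocol's population.

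The cost is wording in Sections 4, 5.2 and 5.4 and one sensitivity table, using data already scheduled. The downsides are possible slight dilution from partly treated participants and reliance on missing at random for early leavers. The 0.9 to 2.0 points remaining when stopping depends on unseen outcomes would go only if MSQOL-54 were collected at Week 52 from those who leave. That would need a protocol clarification and is not part of this change.

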## 5. STATISTICAL ANALYSES

### 5.1. General Considerations

The final planned primary analyses will be performed after the completion of the following sequential steps:

1. All participants have completed (or withdrawn from) the study as defined in the protocol.
2. All required database cleaning activities have been completed and final database release and database lock has been declared by Data Management.

#### 5.1.1. General Methodology

Unless otherwise stated, all hypotheses will be tested at a 2-sided significance level of 0.05 and 95% confidence interval. All continuous measurements will be summarised descriptively at each visit by treatment using observed data.

Summary of continuous variables will be presented using N, Mean, 95% confidence interval of mean, Standard Error of mean (SE), Standard Deviation (SD), Median and Range (Minimum and Maximum). The categorical variables will be presented using number and percentage based on N.

For measurements over time mean values will be plotted to explore the trajectory over time. Observed data will be used as the basis for plotting data along with bars as +/- SE, not otherwise specified.

As a primary analysis, a standard Analysis of Covariance (ANCOVA) will be applied for primary and secondary endpoint to test the significance of the effects of the treatment at Week 52. The model includes treatment as fixed factor and the corresponding baseline value as a covariate.

A parametric Repeated Measures Analysis (RMA) Model will be applied as a secondary analysis to test the significance of the effects of the treatment at Week 4, Week 8, Week 16, Week 24, Week 32, Week 42 and Week 52 including baseline as covariate.

Presentation of results from a statistical analysis model will include the estimated mean treatment effects (Least Square Means (LSMeans)). For all endpoints analysed statistically, estimated mean treatment differences will be presented together with two-sided 95% confidence intervals and p-values,

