Randomization will be conducted using the REDCap randomization module. REDCap does not use an algorithm to dynamically randomize subjects, but rather a pre-determined, stratified, and permuted randomization schedule. The module allows for creating a custom allocation list, which serves as a lookup table for deciding how to randomize subjects. The allocation table is stratified to achieve even study treatment distribution within the following subgroups. Raw coded values corresponding to the table are in parenthesis following their representative category.

- Multiple's sclerosis severity (Mild vs Moderate):
 - **Mild disability (1)** (EDSS < 4)
 - **Moderate disability (2)** (EDSS \geq 4 and < 6.5)
- Age: ≤ 55 (1) vs > 55 (2)
- Gender: Female (1) or Male (2)

1:1 Drug to Control Group Distribution Rule

The allocation table is structured so that there is 1 to 1 respective distribution between drug and control groups.

Modifications to Allocation

There are more permutations assignments created in the allocation table, than the 24 required to accommodate multiple subgroups and support possible drop-out scenarios. Once the randomization model is defined in REDCap, the allocation table will become locked and unmodifiable. If more allocations are necessary, REDCap has the capability to ONLY append to the existing allocation table and not replace it.

Controlling Blinded Information

REDCap system's user privileges can be used to allow only certain users to be able to set up the randomization, perform the randomization, or view the allocation information. All REDCap end users will be blinded and will not have access to the randomization information with exception to the unblinded pharmacist and the personnel who will be responsible in setting up the randomization schedule and performing the randomization.

Blinding for Dose Administration

All subjects, investigators, and site staff will be blinded to treatment assigned.

Amber plastic bags shall be used to cover sodium chloride (saline) bags with the product under investigation for infusion. Only subject identification number and date of birth will be on the bag label, to ensure proper distribution.

For the preparation of the investigational product, Unblinded pharmacist (UP) will inject the investigational product into a 250 ml sodium chloride (Saline) infusion bag, cover it with an amber plastic bag and apply the label before delivering it to study site.

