#### 5.2.2. Main analytical approach

Primary analysis
Endpoint/Variables

 
Change from baseline at Weeks 52 in Multiple Sclerosis Quality of Life (MSQOL)-54 Composite scores following treatment with HB-adMSCs or Placebo.
 

ANCOVA Model Specification

 
To compare the HB-adMSCs to Placebo on Change from baseline to Week 52, a standard Analysis of Covariance (ANCOVA) model will be fitted
 
Terms fitted in the mixed effect model will include: 
 
Primary endpoint efficacy measurements available at - Week 52 will be response variable in a linear mixed model using a variance-covariance residual matrix.
 
The model will include: 
 
Fixed factors: treatment
 
Fixed stratification factors: Multiple's sclerosis severity (Mild disability (EDSS < 4) ; Moderate disability (EDSS > 4 and < 6.5)), Age (< 55 ; > 55) and Gender (Female ; Male)
 
 
 
 
 

• Covariate: baseline

Model Checking and Diagnostics
For the ANCOVA Model assumptions will be checked, and appropriate adjustments may be applied based on the data.
Distribution assumptions underlying the model used for analysis will be examined by obtaining a normal probability plot of the residual and a plot of the residuals versus the fitted values (i.e., checking the normality assumption and constant variance assumption of the model respectively) to gain confidence that the model assumptions are reasonable.
Non-parametric analyses, Mann-Whitney U (or Wilcoxon Rank-Sum) Test will be conducted if the normality assumptions do not hold.
Results presentation
Presentation of results from a statistical analysis model will include the estimated mean treatment effects (Least Square Means (LSMeans)) and estimated mean treatment differences will be presented together with two-sided 95% confidence intervals standard error for mean difference and p-value.
Secondary analysis
Endpoint/Variables
Change from baseline in Multiple Sclerosis Quality of Life (MSQOL)-54 Composite scores following treatment with HB-adMSCs or Placebo at Week 4, Week 8, Week 16, Week 24, Week 32, Week 42 and Week 52.
Repeated Measures Model Specification

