### **6. SAMPLE SIZE DETERMINATION**

Sample size consists of up to 24 subjects who have been diagnosed with Relapsing Remitting Multiple Sclerosis.

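### SAP 5.1.1 leaves the three randomisation factors out of the ANCOVA and repeated-measures models, 5.2.2 puts them in, and no sentence says which section governs

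*SAP*

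**What the plan says.** **SAP 5.1.1, General Methodology.** "As a primary analysis, a standard Analysis of Covariance (ANCOVA) will be applied for primary and secondary endpoint", testing treatment at Week 52. The next sentence gives its content: "The model includes treatment as fixed factor and the corresponding baseline value as a covariate". The RMA is then described with baseline as its only named covariate.

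**SAP 5.2.2, Main analytical approach, under Primary analysis.** "To compare the HB-adMSCs to Placebo on Change from baseline to Week 52, a standard Analysis of Covariance (ANCOVA) model will be fitted". The terms are treatment, baseline and a further line that begins "Fixed stratification factors: Multiple's sclerosis severity (Mild disability" and goes on to age and gender. The repeated-measures specification in the same section carries the same "Fixed stratification factors" line.

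**Protocol, Investigational Product Assignment.** The same three factors define the randomisation: "The allocation table is stratified to achieve even study treatment distribution within the following subgroups".

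**Test level and size.** In SAP 5.1.1, "all hypotheses will be tested at a 2-sided significance level of 0.05 and 95% confidence interval". In SAP section 6, "Sample size consists of up to 24 subjects who have been diagnosed with Relapsing Remitting Multiple Sclerosis". No effect size, standard deviation, power or dropout rate is given.

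**The concern.** Both sections call the Week 52 ANCOVA the primary analysis of the same endpoint, but the model terms differ. Two programmers, each following one section, would report different p-values and confidence intervals.

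Three things are at stake.

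- **Design.** Allocation is balanced within strata. A model without those strata ignores the design, and if the strata predict outcome its standard error is too large.
- **Freedom of choice.** If the question is still open when treatment codes are known, the more favourable model can be picked. SAP 5.2.2 also permits adjustments to the model based on the data, so the plan does little to close this off.
- **Size.** With at most 24 patients, and possibly fewer in an efficacy set that requires all six infusions, a few model terms can move a result across 0.05.

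**Working it through.** **Step 1. Is there a tie-break in the text?** The opening qualifier in 5.1.1 (unless otherwise stated) is attached to the significance level, not to the model. Section 5.1.1 does not refer forward to 5.2.2. The protocol's Statistical Methods name only a repeated-measures mixed model and list no covariates, so they cannot settle the matter. The programming specification is cited for displays, not for model terms. No sentence sets precedence.

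**Step 2. Residual degrees of freedom.** df = N − number of fitted coefficients. Without strata there are 3 (intercept, treatment, baseline); with strata there are 6.

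- N = 24: 24 − 3 = 21 (critical t 2.080) against 24 − 6 = 18 (2.101).
- N = 20: 20 − 3 = 17 (2.110) against 20 − 6 = 14 (2.145).

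The three extra terms raise the critical value by about 1% at N = 24 (2.101 / 2.080 = 1.010).

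**Step 3. Direction of the effect.** Let R² be the share of post-baseline-adjustment variance explained by the strata. With perfect balance within strata, the model without strata overstates the standard error by 1/√(1 − R²). At R² = 0.30 this is 1/√0.70 = 1.195. Real balance is weaker, because three binary factors make 8 cells averaging 24/8 = 3 patients, so a simulation is needed.

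**Step 4. Simulation at N = 24.** There were 6,000 trials per row, with both models fitted by least squares to the same data. These inputs are assumed, not taken from the documents: permuted blocks of 4 in each cell, factor prevalences 0.60/0.40/0.25, SD 1 after baseline, and the effects and R² shown. Monte Carlo standard error is √(0.05 × 0.95/6000) = 0.3 points near 5% and √(0.5 × 0.5/6000) = 0.6 points near 50%.

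| Effect (SD) | R² | Significant, no strata | Significant, with strata | Models disagree | Either significant |
|---|---|---|---|---|---|
| 0 | 0 | 5.0% | 5.0% | 1.9% | 6.0% |
| 0 | 0.15 | 3.4% | 4.8% | 3.0% | 5.6% |
| 0 | 0.30 | 2.8% | 5.0% | 3.7% | 5.8% |
| 0.8 | 0 | 44.2% | 41.4% | 7.7% | 46.6% |
| 0.8 | 0.15 | 44.2% | 48.0% | 11.6% | 51.9% |
| 0.8 | 0.30 | 43.2% | 54.8% | 17.7% | 57.9% |
| 1.2 | 0 | 78.7% | 75.7% | 6.6% | 80.5% |
| 1.2 | 0.15 | 79.1% | 81.3% | 8.4% | 84.4% |
| 1.2 | 0.30 | 79.0% | 88.2% | 12.4% | 89.8% |

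At N = 20, picking the smaller p-value gives 5.8 to 6.9% type I error, and the models disagree in 9.8 to 17.8% of trials at 0.8 SD.

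**Step 5. Power at an effect of 1.0 SD, N = 24, same block size.**

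| R² | No strata | With strata |
|---|---|---|
| 0 | 63% | 59% |
| 0.10 | 63% | 64% |
| 0.20 to 0.30 | 62–63% | 68–74% |

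The models break even at an R² of roughly 0.05 to 0.10: in a further set of 5,000 trials per cell, power without and with strata was 62.6% and 61.4% at 0.05, and 61.9% and 62.7% at 0.10. Disagreement at this effect runs from about 9 to 17%.

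**The case against.** The strongest reply is that a careful programmer would use 5.2.2 anyway. It is the endpoint-specific section and itemises every term, whereas 5.1.1 is general text that never says other terms are excluded. Both Bayesian model equations include the three strata. Section 5.3.1 sends the secondary endpoints to 5.2.2 for their models. This stands as evidence of intent and is the reason to resolve the conflict in favour of 5.2.2. It remains an inference, because the SAP does not state the convention on which it relies.

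A reader might also infer more than the documents support:

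- **That a single confirmatory test exists in two versions.** SAP 5.2.1 and 5.2.2 give two composite scores, physical and mental, so there are at least two primary p-values under either model. The Holm adjustment in 3.1 covers secondary endpoints only. That is a separate and plainer threat to the 5% level.
- **That using 5.1.1 would inflate false positives.** It does the reverse: the test becomes conservative when the strata matter.
- **That power is lost whatever the data.** This depends on R², which the documents do not give. At R² = 0 the model without strata is slightly the more powerful.
- **That the models often disagree.** The higher figures require a large true effect. Under the null, disagreement is only 2 to 4%.

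**Conclusion.** The inconsistency is real and worth correcting before unblinding, but it is modest. The two sections give different terms for the same primary ANCOVA and the same RMA, and precedence is implied rather than stated.

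If 5.1.1 were programmed and the strata explained 20 to 30% of the variance left after baseline, type I error would fall to about 3%, and power at 1.0 SD would drop by about 6 to 12 points (62 against 68, up to 62 against 74). Leaving the choice open until results are seen gives about 6% type I error for each composite score, a small inflation from this source alone.

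These sizes rest on assumed block size, prevalences, effect and R². The textual conflict does not depend on them.

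**What to change.** Before unblinding, amend the SAP as follows.

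1. In 5.1.1, replace the model sentence so that the terms are *treatment, the corresponding baseline value and the three randomisation strata, as specified in 5.2.2*, for both the ANCOVA and the RMA.
2. State that 5.2.2 governs, and label any model without the strata as a sensitivity analysis.
3. Define the strata in 5.2.2 by the categories of the protocol's allocation table. As printed, 5.2.2 leaves EDSS exactly 4 and age exactly 55 in no category. The equality signs may have been lost in reading the PDF, so check the source file. Separately, both documents cap the moderate category below 6.5 while inclusion criterion 5 admits 6.5. For the analysis, place such patients in the category in which they were randomised.
4. In 5.1.1, drop the secondary endpoints from the ANCOVA sentence, or otherwise reconcile it with 5.3.1, which makes the RMA primary and the ANCOVA secondary for those endpoints.

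The cost is a few sentences and no new data. The statistical price is three residual degrees of freedom, or about 3 to 4 points of power at N = 24 if the strata carry no information.
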